The type (i.e., the international nonproprietary name, the dose, and the projected last dose of all antiplatelet agents) must be predeclared at randomization. ASA 75-100 mg/day or generic/branded clopidogrel 75 mg/day (chronic therapy following loading dose) are the preferred agents. Type, dose, and (projected) last dose may be changed during the treatment period for documented medical reasons.

Study Duration:

Subjects will be monitored throughout the entire study period regardless of whether they have or have not experienced an endpoint. Monitoring will be performed with study visits (which can be on-site or at the subject's current place of living, but the monitoring will be conducted by the Investigator or qualified designee) at 3 and 6 months post randomization, then semi-annually, at the end of the treatment period, and at 30 days after the last dose of the study medication (see [Table 17.1](#)). After the End of Treatment Visit, subjects will have the option to be followed by telephone contact with the site and/or review of their

medical records by qualified site personnel until the end of the study (common study end date [CSED]).

The enrollment will be stopped no later than at the attainment of a total of 320 subjects experiencing an adjudicated NACE across the combined treatment arms, and the study will continue until the last subjects enrolled will have accomplished the minimum treatment duration of at least 6 months plus their Post-treatment Follow-up Visit.

Study Sites and Locations: It is planned to enroll approximately 1400 subjects with a 1:1 randomization ratio (Edoxaban: VKA) approximately 200 study sites located in the USA, Canada, Europe (Austria, Belgium, France, Germany, Italy, the Netherlands, Spain, Switzerland, UK and potentially other countries), and Japan. Other countries may also participate.

Planned Sample Size: The primary endpoint is NACE.

In order to determine the sample size, the following assumptions were made:

- *Event rate:* Based on published literature and results from the ENGAGE AF-TIMI 48 study, it is assumed that the event rate of the primary efficacy endpoint of NACE in AF-subjects treated post TAVI with VKA would be 14%/year.

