5.2.1.2. VKA

Any oral VKA tablet of choice for use in accordance with the local label to obtain an INR of 2.0 to 3.0 (numbers inclusive) [Japan: 1.6 to 2.6 in subjects aged ≥ 70 (numbers inclusive)]

It is the responsibility of the Investigator to collect INR at study visits, and in between study visits (preferably monthly), as needed per standard of care, in order to maintain INR within the target range. The Investigator will monitor the INR and adjust the VKA dose to maintain the INR within target (2.0 to 3.0 (numbers inclusive) [Japan: 1.6-2.6 in subjects aged ≥ 70 (numbers inclusive)]), unless performed by the subject's treating physician. The Investigator will record any changes in VKA dosage within the eCRF.

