6.4. Continued Treatment Visits

For all subjects randomized to VKA, all INR measurement shall be performed by local accredited/certified labs at a frequency determined by the subject's treating physician (monthly preferred). Trained and certified subjects may perform INR testing themselves using an approved point-of-care device but need to provide the results to the Investigator and the results need to be recorded in the eCRF.

- Dose adjustments in VKA will be made to achieve and maintain an INR of 2.0 to 3.0 (numbers inclusive) [Japan: 1.6 to 2.6 in subjects aged ≥ 70 (numbers inclusive)] throughout the study.

For all subjects, study visits (either as on-site or at the subject's current place of living, must be conducted by the Investigator or their appropriately trained designee) at 3 months (± 14 days), 6 months (± 14 days), and at 6 month intervals (± 14 days) thereafter through the end of the study which may be 36 months or longer (i.e., event driven study).

The following procedures will be performed during study visits:

- Check and record any changes in concomitant medication
- Assessment and recording of (S)AEs and suspected clinical events since last visit
- Assessment of any hospitalization for cardiovascular causes (such as shock, arrhythmia, cardiac rupture, stroke, aneurysms, stent occlusions, etc.) or bleeding
- Record vital signs (blood pressure and heart rate after the subject has been resting at least 5 minutes in a sitting position; body temperature and weight)
- Only if medically necessary, 12-lead ECG and recording of the results
- For childbearing potential female subjects, a urine pregnancy test (e.g., dipstick test) will be performed at 3 months, 12 months, 24 months, and End of Treatment

Visits. Furthermore, pregnancy tests will be carried out whenever there are clinical indications for the existence of a pregnancy.

- Blood draw for analysis by an accredited/certified local laboratory for all subjects (see Section 9.9) or if results are available from standard of care and are within 15 days prior to the visit these values may be used instead of requiring an additional blood draw.
 - *The liver function panel needs to be run at the 6 Month and 12 Month Visits and if clinically necessary at other times.*

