9.1. Adverse Event Collection and Reporting

All clinical AEs (see Section 9.3.1 for definitions) occurring after the subject signs the Informed Consent Form and up to 30 days after the last dose of study medication (i.e., the follow-up period), whether observed by the Investigator or reported by the subject, will be recorded on the Adverse Event eCRF page.

Subjects who permanently discontinue study medication but continue in the study will be followed up every 6 months for collection of vital status (not vital signs) including collection of SAE and/or endpoint event reporting until the end of study (see Section 6.7).

Medical conditions (including laboratory values/vital signs that are out of range) that were diagnosed or known to exist prior to Informed Consent will be recorded as part of medical history.

All serious adverse events (SAEs), are to be reported according to the procedures in Section 9.6.

- All laboratory results, vital signs, ECG, and any other imaging results or findings should be appraised by the Investigator to determine their clinical significance. Isolated abnormal laboratory results, vital sign findings, or ECG findings (i.e., not part of a reported diagnosis) should be reported as AEs if they are symptomatic, lead to study drug discontinuation, dose reduction, require corrective treatment, or constitute an AE in the Investigator's clinical judgment.
- At each visit, the Investigator or qualified designee will determine whether any AEs have occurred by evaluating the subject. Adverse events may be directly observed, reported spontaneously by the subject, or by questioning the subject at each study visit. Subjects should be questioned in a general way, without asking about the occurrence of any specific symptoms. The Investigator must assess all AEs to determine seriousness, severity, and causality, in accordance with the definitions in Section 9.3. The Investigator's assessment must be clearly documented in the site's source documentation with the Investigator's signature.

Always report the diagnosis as the AE or SAE term. When a diagnosis is unavailable, report the primary sign or symptom as the AE or SAE term with additional details included in the narrative until the diagnosis becomes available. If the signs and symptoms are distinct and do not suggest a common diagnosis, report them as individual entries of AE or SAE.

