9.5. Reporting SAEs/AEs

9.5.1. Documentation

To effectively evaluate the safety profile of the study treatments, this study will report all (S)AEs occurring after the subject signs the IC and as long as the subject remains in the study or until the study is terminated by the Sponsor (i.e., the end of the study), whether observed by the Investigator or reported by the subject. All AEs will be recorded on the AE/Outcome eCRF page(s) and include:

- Any components of the study endpoint assessments (see Section 7);
- AEs that meet seriousness criteria (see Section 9.3.4);
- AEs that result in interruption or discontinuation of the assigned study treatment;
- Any other AE.

All laboratory results and vital signs should be evaluated by the Investigator regarding clinical significance. Isolated abnormal laboratory results or vital sign findings that are not part of a diagnosis should be reported as AEs or SAEs. Medical conditions (including laboratory values/vital signs that are out of range) that were diagnosed or known to exist prior to IC will be recorded as part of medical history.

All SAEs are to be reported as long as the subject remains in the study or until the study is terminated by the Sponsor (i.e., the end of the study) and according to the procedures in Section 9.6. Always report the diagnosis as the AE or SAE term. When a diagnosis is unavailable, report the primary sign or symptom as the AE or SAE term with additional details included in the narrative until the diagnosis becomes available. If the signs and symptoms are distinct and do not suggest a common diagnosis, report them as individual entries of AE or SAE. For events that are serious due to hospitalization, the reason for hospitalization must be reported as the SAE (diagnosis or symptom requiring hospitalization).

AEs may be directly observed, reported spontaneously by the subject or by questioning the subject at each study visit. Subjects should be questioned in a general way, without asking about the occurrence of any specific symptoms. The Investigator must assess all AEs to determine seriousness, severity, and causality, in accordance with the definitions in Section 9.3.5 and Section 9.3.6. The Investigator's assessment must be clearly documented in the site's source documentation with the Investigator's signature.

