9.9. Clinical Laboratory Evaluations

Information will be entered in the case report form on whether or not measured, date of measurement, and measurement results and the local laboratory ranges for the following items.

The results will be reviewed and compared to the local accredited/certified laboratory's normal ranges. The visits at which these samples will be collected are shown in the schedule of assessments (Table 17.1).

The following safety laboratory evaluations are performed:

- **Serum Chemistry Panel**
 - Creatinine
 - Sodium (Na⁺)
 - Potassium (K⁺)
 - Chlorine (Cl⁻)
 - Blood urea nitrogen (BUN)
 - Glucose
- **Complete Blood Count (CBC) Panel:** Including Hemoglobin, Hematocrit, WBC, Platelet Count
- **INR** (only for subjects on VKA)
- **Urine pregnancy test** (e.g., dipstick test), for childbearing potential female subjects at Randomization, 3 months, 12 months, 24 months, and End of Treatment Visits.
- **Serum pregnancy test** at time of Screening for women of child bearing potential who are female subjects who are of child bearing potential.

A liver function panel (total bilirubin [conjugated/unconjugated performed when total serum bilirubin \geq 2 mg/dL], ALT, AST, ALP) will be performed at Screening (only if a recent, within the 15 days before randomization, is not available), and at the 6 Month and 12 Month Visits.

All other assessments are collected from local laboratory results for tests done as part of routine care. Local laboratory assessments are used for parameters required to verify eligibility and for parameters that require monitoring according to local routine.

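### Unprompted questioning also governs endpoint bleeding, and only VKA subjects have INR checks between visits, so fuller capture of non-admitted major bleeds in the VKA arm cannot be excluded.

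*Combined protocol and SAP*

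**What the plan says.** **Elicitation.** Section 9.1, on adverse event collection, states: "Subjects should be questioned in a general way, without asking about the occurrence of any specific symptoms". Section 9.5.1 repeats the sentence and lists among the adverse events to be recorded "Any components of the study endpoint assessments (see Section 7". The opening of Section 9 places bleeding endpoints on the AE/Outcome pages, and Section 9.1.1 has every bleed reported as an AE or SAE. None of these sections exempts endpoints from the questioning rule.

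**Visits, both arms.** Section 6.4 schedules visits "at 3 months (± 14 days), 6 months (± 14 days), and at 6 month intervals (± 14 days) thereafter". Each visit includes "Assessment of any hospitalization for cardiovascular causes" or bleeding, an assessment of suspected clinical events, and a blood draw. The panel in Section 9.9 includes hemoglobin.

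**Between visits.** Section 5.2.1.2 makes the Investigator responsible "to collect INR at study visits, and in between study visits (preferably monthly), as needed per standard of care". In the laboratory list of Section 9.9, INR is "only for subjects on VKA". No interim contact is scheduled for edoxaban subjects on treatment.

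**The concern.** The trial is open-label (Section 5.1.3), and the blinded Clinical Events Committee can adjudicate only what sites report. A bleed that never reaches the site is analysed as event-free time, and Section 11.2 allows no imputation.

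Unprompted questioning suits unsolicited adverse events, because it avoids suggesting symptoms. It suits a primary endpoint less well, especially when one arm has extra occasions on which a bleed may come to light. If VKA bleeds are captured more fully, the observed hazard ratio falls. That makes noninferiority on NACE and on major bleeding easier to declare, and likewise the two superiority claims. Under-reporting that differed in this way would be anti-conservative at every step of the hierarchy in Section 11.4.1.

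**Working it through.** The plan gives no figure for event capture, so there is nothing of its own to reproduce. The check has two parts.

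**1. Routes by which a major bleed reaches the site**

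| Route | Arms | What it covers |
|---|---|---|
| Open question (9.1, 9.5.1) | Both | What the subject volunteers |
| Hospitalization prompt (6.4) | Both | Admitted events; Section 7.4.3 defines an admission as a stay of at least 24 h |
| Suspected clinical events (6.4) | Both | Required, but no question list or method |
| Visit blood count (6.4, 9.9) | Both | May come up to 6 months after the bleed; Table 17.2 also requires overt bleeding |
| Reporting outside visits (Table 17.1, note k) | Both | Begins once site staff learn of the event |
| Interim INR checks (5.2.1.2, 6.4) | VKA only | An extra occasion for a bleed to surface |

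The exposed group is narrow: overt bleeds that meet Table 17.2 through a hemoglobin fall of 2 g/dL or a transfusion of 2 units, managed without admission.

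To month 24 each arm has 5 post-baseline visits (months 3, 6, 12, 18, 24). Monthly INR would add about 24 checks in the VKA arm, some coinciding with visits. The number is smaller if the treating physician tests less often.

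**2. What a given capture difference would do**

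Inputs from the plan: two-sided 95% confidence interval (one-sided 2.5%), noninferiority bound 1.38, superiority bound 1.00, 1:1 allocation, 320 NACE (Sections 11.4.1, 5.1.2 and 11.9).

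Assumed, because the documents give no values: relative under-capture of bleeding in the edoxaban arm u = 5% or 10%; number of major bleeds D = 100 or 200; bleeding share of first NACE f = 30% or 50%.

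Model: observed HR = true HR × (1 − u), and SE of log HR = 2/√D. With the true HR on the boundary, the boundary cancels, so one formula serves the 1.38 and the 1.00 tests:

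error = Φ(−1.96 − ln(1 − u) × √D/2)

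Major bleeding:
- D = 100, u = 5%: Φ(−1.96 + 0.0513 × 5) = Φ(−1.704) = 4.4%
- D = 100, u = 10%: Φ(−1.96 + 0.1054 × 5) = Φ(−1.433) = 7.6%
- D = 200, u = 5%: Φ(−1.96 + 0.0513 × 7.071) = Φ(−1.597) = 5.5%
- D = 200, u = 10%: Φ(−1.96 + 0.1054 × 7.071) = Φ(−1.215) = 11.2%

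NACE noninferiority, replacing u by f × u and D by 320 (√320/2 = 8.944):
- f = 30%: 3.4% (u = 5%), 4.6% (u = 10%)
- f = 50%: 4.2% (u = 5%), 6.7% (u = 10%)

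With u = 0, every result returns to 2.5%.

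**The case against.** The strongest reply is that the open question is only one route among several. Every visit in both arms requires assessment of suspected clinical events and of bleeding-related hospital stays, a hemoglobin measurement, and a review of medication changes and interruptions. Table 17.1, note k, asks for endpoint reporting at any time. A reader might infer that an outpatient major bleed is found only if the subject volunteers it; these provisions do not support that. A measured 2 g/dL fall or a 2-unit transfusion also implies medical care and a record. The bleeds most dependent on prompting are minor ones, which enter none of the four hypotheses.

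A reader might also set about 24 VKA contacts against 5 for edoxaban. The documents do not support that as a count of endpoint contacts. Monthly INR is a preference. Section 6.4 mandates a measurement at a visit only if the last is more than 3 months old or the target has proved hard to reach. Table 17.1, note h, allows testing by a general practitioner, an anticoagulation clinic or the subject's own device. Nothing says that bleeding is asked about at an INR check. Edoxaban subjects also have tablet counts (Section 5.5), which may reveal interruptions.

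Finally, eCRF pages, data-entry guidelines and the adjudication charter may already contain structured prompts, and they are not part of these documents.

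Most of this stands and narrows the point. It does not remove it. The only stated questioning method excludes specific symptoms, no endpoint exception is written, and tablet counts take place at scheduled visits, so they add no contact in between.

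**Conclusion.** The point holds in limited form. The written questioning rule covers endpoint bleeding, and the only arm-specific interim checks are in the VKA arm. Fuller VKA capture of non-admitted ISTH major bleeds therefore cannot be excluded. If present, it would favour edoxaban in both noninferiority and both superiority tests.

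The documents do not show that such a bias exists, and they give no means of sizing it. The 4–11% range for major bleeding rests wholly on the assumed 5–10% under-capture and 100–200 bleeds. It applies per test: superiority on major bleeding is reached only after both noninferiority tests succeed, so these are not trial-wide error rates. The model also treats a missed bleed as lost. In a subject with a later qualifying event, the first event is delayed rather than lost, which would lessen the effect.

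**What to change.** - In Sections 9.1 and 9.5.1, limit the open-question sentence to adverse events that are not endpoint components.
- Add one scripted endpoint checklist, identical in both arms, at every existing scheduled visit and at the 6-monthly calls of Section 6.7. It would cover any bleeding, transfusion, hemoglobin drop, hospital or emergency stay, stroke-like symptoms, myocardial infarction, embolism and valve problems.
- Record how each event was first detected (scheduled contact, INR check, other) and tabulate this by arm, descriptively. Do not plan a repeat of the primary tests with INR-detected events deleted. Only the VKA arm can have such events, so this would remove true events from one arm and raise the hazard ratio by construction.

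The cost is one eCRF page and a few minutes per visit or call, with no added visits. More minor bleeds will be reported in both arms. The checklist lessens the effect of unequal interim contact but does not remove the inequality.

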9.1.1. Bleeding

All bleeding events will be reported in the eCRF as either an AE or SAE depending upon the seriousness criteria (see Section 9.6 for additional details).

Bleeding requiring medical attention will be adjudicated by the CEC based on ISTH (see Section 17.1.1). Bleeding events that do not require medical attention will be classified as minor bleeding without CEC adjudication.

The CEC will require all available details about the bleeding event and related information to allow successful objective adjudication of the event. Details may include, but are not limited to, information such as the following:

- Location of the bleeding
- Timing of the bleeding event: association with adherence of study drug, medications, and procedures

- Treatment for bleeding event, including notes or summary of the recommendations from a healthcare professional from whom medical treatment was obtained
- Magnitude of the bleeding (including size if skin or subcutaneous hematoma)
- Hemoglobin levels at randomization and at the time of the bleeding event, lowest value, pre- and post-transfusion values, and after resolution of the bleeding event
- Diagnostic tests for the evaluation of the bleeding such as endoscopy (gastrointestinal bleed), ear, nose, and throat consult (ear, nose, throat bleed), urology consult (hematuria or urogenital bleeding), surgical consult (skin and soft tissue, including intraabdominal bleeding), gynecological consult (uterine or vaginal bleeding), neurological consult (intracranial bleed), or ophthalmology consult (intraocular bleed)
- Diagnostic scans (CT scans or MRIs), ultrasounds, or x-rays performed to evaluate the bleeding (intracranial bleed)
- Any other information that can be of help to the CEC to allow successful objective adjudication of the bleeding event.

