5.1.3. Blinding

This study is open-label.

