15.10. Clinical Events Committee

An independent study specific CEC will review and adjudicate key endpoint events as outlined in the CEC Charter.

The CEC will comprise qualified judges, who are not Investigators in the study and not otherwise directly associated with the Sponsor. The CEC judges will remain blinded to treatment throughout the adjudication process and the study. The CEC-adjudicated data will be used in the final efficacy and safety analyses. The CEC and the events it will adjudicate will be detailed in the CEC Charter.

The Investigator/investigational site will supply the CEC with whatever information that is requested such that the CEC will be able to perform their adjudication duties.

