17.1. Bleeding Criteria

17.1.1. ISTH Bleeding Criteria

Table 17.2: ISTH Bleeding Criteria²⁷

ISTH Bleeding Criteria

Major bleeding
 
 • Clinically overt bleeding that is associated with: 
 ○ A fall in hemoglobin of 2 g/dL (1.24 mmol/L) or more, or ○ A transfusion of 2 or more units of whole blood or packed red blood cells, or ○ Symptomatic bleeding in a critical site or organ such as: intracranial, intraspinal, intraocular, retroperitoneal, pericardial, intra-articular, intramuscular with compartment syndrome, or ○ A fatal outcome

Clinically relevant non-major (CRNM) bleeding
 
 • Any sign or symptom of hemorrhage (e.g., more bleeding than would be expected for a clinical circumstance, including bleeding found by imaging alone) that does not fit the criteria for the ISTH definition of major bleeding but does meet at least one of the following criteria: 
 ○ requiring medical intervention by a healthcare professional ○ leading to hospitalization or increased level of care ○ prompting a face to face (i.e., not just a telephone or electronic communication) evaluation.

Minor
 
 • Bleeding episodes not requiring any medical attention and therefore not meeting the criteria for major or clinically relevant non-major bleeding.

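### The rule in Section 9.1.1 that sends only bleeds requiring medical attention to the CEC can leave an ISTH major bleed, defined by its hemoglobin fall, filed as minor without blinded review

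*Combined protocol and SAP*

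**What the plan says.** Section 9.1.1 of the protocol sets the routing rule in two sentences. "Bleeding requiring medical attention will be adjudicated by the CEC based on ISTH". The remainder bypasses the committee: "Bleeding events that do not require medical attention will be classified as minor bleeding without CEC adjudication". The same section says how bleeds enter the database: "All bleeding events will be reported in the eCRF as either an AE or SAE depending upon the seriousness criteria". It does not say who decides whether a bleed required medical attention.

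Table 17.2 (Section 17.1.1) defines major bleeding as clinically overt bleeding that meets any one of four limbs. The first is "A fall in hemoglobin of 2 g/dL (1.24 mmol/L) or more, or". The others are transfusion of two or more units, symptomatic bleeding in a critical site, and a fatal outcome. The Minor row of the table reads: "Bleeding episodes not requiring any medical attention and therefore not meeting the criteria for major or clinically relevant non-major bleeding".

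Three other places bear on the point. Section 5.1.3 states: "This study is open-label". The closing paragraph of Section 7.4.3 says that the CEC adjudicates all relevant NACE components blind. Section 15.10 states: "The CEC-adjudicated data will be used in the final efficacy and safety analyses". It leaves the list of adjudicated events to the CEC Charter. Sections 11.4 and 11.4.1 analyse time to first event as adjudicated by the CEC.

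**The concern.** The gate and the endpoint use different criteria. The gate asks whether the bleed required medical attention. The endpoint asks about hemoglobin, transfusion, site and death. Where the two disagree, the gate acts first, and a bleed stopped there is never classified by the committee whose classification the analysis uses.

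The protocol names no decision-maker. Because bleeds are entered in the eCRF, it is presumably the site, which knows the treatment arm. If so, an unblinded judgement comes before the blinded one for some events of the primary safety endpoint, which is tested for noninferiority in Step 2 and superiority in Step 3 and also feeds NACE in Steps 1 and 4. Blinded endpoint evaluation is the main safeguard of an open-label design of this kind.

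Unequal filtering between arms is plausible. Sections 5.2.1.2 and 6.4 call for INR testing in VKA subjects, preferably monthly, while study visits for everyone fall at 3 and 6 months and then every 6 months. More contact could make a VKA bleed more likely to be evaluated and referred. That is an inference; the documents establish neither the direction nor the size.

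**Working it through.** **Step 1: compare each major limb of Table 17.2 with the gate in Section 9.1.1.**

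| Limb | Can it be met without medical attention? |
|---|---|
| Overt bleed with hemoglobin fall of 2 g/dL or more | Yes. The fall may be seen only on a scheduled blood count. |
| Transfusion of 2 or more units | No. Transfusion is itself medical attention. |
| Symptomatic critical-site bleed | Rarely. The definition does not require attention, but such bleeds almost always receive it. |
| Fatal outcome | Possible. The death still counts in NACE, but the event could be missed as a major bleed. |

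The exposed case is essentially the first limb: an overt, self-limited bleed with a qualifying fall on a scheduled count. The data to detect it exist, since Section 6.4 has blood drawn at study visits for all subjects and the blood count panel in Section 9.9 includes hemoglobin. No section of the protocol states a trigger by which such a fall overrides the gate.

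**Step 2: does the Minor row close the gap?** It infers from the absence of medical attention that the major criteria are not met. For the transfusion limb that inference is sound. For the hemoglobin limb it is not, because nothing in the major row links the fall to medical attention. An overt bleed of this kind satisfies the major row and the premise of the Minor row together.

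**Step 3: size, for illustration only.** The plan gives no figure to reproduce here: no expected number of major bleeds and no share of bleeds not referred. Both are assumed.

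Inputs: D = 150 true major bleeds (range 100 to 200), equally split; mE and mV = the shares of true major bleeds lost at the gate in the edoxaban and VKA arms.

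- Multiplier on the observed hazard ratio: f = (1 − mE)/(1 − mV)
- Events left: d = D × [1 − (mE + mV)/2]
- Standard error of the log hazard ratio: SE = 2/√d
- One-sided error of Step 3 when the true hazard ratio is 1: Φ(−1.96 − ln f/SE)

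Worked for mE = 2%, mV = 1%: f = 0.98/0.99 = 0.990 and ln f = −0.0102; d = 150 × 0.985 = 147.75; SE = 2/√147.75 = 0.165; error = Φ(−1.96 + 0.062) = 2.9%.

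| Lost, edoxaban / VKA | f | Error, D = 150 | Error, D = 100 to 200 |
|---|---|---|---|
| Equal in both arms | 1.000 | 2.5% | 2.5% |
| 2% / 1% | 0.990 | 2.9% | 2.8% to 3.0% |
| 1% / 2% | 1.010 | 2.2% | 2.2% to 2.1% |
| 10% / 5% | 0.947 | 5.0% | 4.5% to 5.6% |
| 5% / 10% | 1.056 | 1.1% | 1.3% to 1.0% |

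The same multiplier applies at the noninferiority boundary. If the true hazard ratio is 1.38, the error of Step 2, taken alone, takes the same values.

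**The case against.** The best defence is that Section 9.1.1 only applies the Minor row of Table 17.2, so the protocol is consistent with itself. It is consistent between those two places, but both conflict with the hemoglobin limb of the major row.

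A second defence is that the route is narrow. This stands. Two of the four limbs are met almost only with medical attention, and a fatal bleed still counts in NACE as a death. Any bleed that prompts face-to-face evaluation or intervention by a healthcare professional is already at least clinically relevant non-major. Section 9.1 has the investigator appraise every laboratory result, so an overt bleed discussed at a visit with a 2 g/dL fall may well be treated as needing attention and referred. A reader might infer that such a bleed never reaches the CEC. The documents do not support that; they show only that the rule as written does not require it to.

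Third, the CEC Charter may contain a hemoglobin or critical-site trigger. This also stands, since the Charter cannot be seen. Nothing in the protocol points to one, and its explicit rule runs the other way.

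Fourth, a reader might infer a bias in favour of edoxaban that doubles the error rate or worse. That needs 10% or more of all edoxaban major bleeds to be lost, with a smaller loss on VKA. The documents give no such share, and the reverse pattern makes the test conservative.

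Finally, blinded adjudication is not the only protection. Both arms share one visit and blood-count schedule, the ISTH criteria are largely objective, and monitors check source records. These reduce the risk but do not route a missed bleed to the committee.

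**Conclusion.** The inconsistency is real and limited. As written, Section 9.1.1 and the Minor row of Table 17.2 allow an overt bleed that meets the hemoglobin limb of ISTH major bleeding to be classed as minor without blinded review, contrary to the statement in Section 7.4.3. The exposed share is probably small. Equal loss in both arms costs events but does not bias the hazard ratio. At 2% against 1% the one-sided error of the superiority test on bleeding shifts by a few tenths of a percentage point; at 10% against 5% it becomes about 5% or about 1%, depending on which arm loses more.

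These sizes rest on assumed event counts and assumed losses, and the direction cannot be determined. The conclusion also assumes that the site makes the call and that the Charter adds no trigger. The point is worth correcting because it concerns a co-primary endpoint and is cheap to close, not because a material bias has been shown.

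**What to change.** Amend Section 9.1.1 and the Minor row of Table 17.2 so that any reported bleed goes to the CEC, regardless of medical attention, if it has any of the following:

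- a hemoglobin fall of 2 g/dL or more on available values
- any transfusion
- a critical site
- a fatal outcome

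Only bleeds with none of these, and no medical attention, would be classed as minor without the CEC. In subjects with a reported bleed, flag hemoglobin falls by program from the blood counts already collected, and leave it to the CEC to decide whether the fall belongs to the bleed. Align Section 7.4.3 and the CEC Charter with the new wording; if the Charter already holds such a trigger, state it in the protocol.

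The cost is a database check and a few more dossiers, with no new tests. Some dossiers will concern falls unrelated to the bleed, especially once visits are six months apart. The change does not remove the earlier step at which the open-label site reports the bleed at all.
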